
• Summary measures of palbociclib treatment patterns, including:
○ Starting dose.○ Proportion of patients with dose reductions at 1, 2 and 3 years after initiation.○ Proportion of patients with palbociclib treatment discontinuation at 1, 2 and 3 years after initiation.○ Mean (Standard Deviation [SD]) dose intensity over the course of treatment in patients who complete treatment of palbociclib○ Median time to dose reduction in number of days (from start of treatment) and in terms of number of cycles (completed or interrupted).○ Median time to dose increase in number of days (from start of treatment) and in terms of number of cycles (completed or interrupted); only in patients with previously reduced dose○ Median time to palbociclib discontinuation ('drug survival') in number of days (from start of treatment) and in terms of number cycles (completed or interrupted).○ Reasons for discontinuation.○ 1st, 2nd and 3rd line of treatment after progression: number of patients prescribed each medication, dose, and length of treatment.• Description of the number of patients which are being prescribed as per posology of treatment (19):
○ Proportion of patients who complete a 28-day cycle (21 days daily dose followed by 7 days off treatment).○ Mean (SD) of completed 28 day cycles.○ Proportion of patients co-administered letrozole at palbociclib initiation.○ Proportion of patients co-administered fulvestrant at palbociclib initiation.	
• Palbociclib: date on initiation, initial dose, date of dose reduction, subsequent dose, dates of cycle initiation and completion, date of discontinuation (indicate whether last cycle is interrupted or completed), reasons for palbociclib dose reduction / increase / discontinuation.• Date of start and end of concomitant medication treatment: letrozole, fulvestrant, osteo-strengthening drugs (denosumab, zometa), other drugs.• First 3 lines of medication after palbociclib discontinuation: name, dose and length of treatment.

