6 ENDPOINTS AND COVARIATES

The following endpoints will be estimated for the final report. Additional endpoints evaluated as a result of decisions made by the CI and Pfizer have been italicized. This list is designed to reflect the analyses conducted.

Primary Objective: To describe patient demographic and clinical characteristics at initiation of palbociclib.

- Age at initiation of palbociclib.
- Distribution of treatment lines
- Time to letrozole – 1st line palbociclib group
- Sex (male/female)
- Ethnicity of patients initiated on palbociclib.
- Menopausal status at initiation of disease
- Menopausal status at recurrence of disease
- Menopausal status at diagnosis of metastatic disease
- Disease free interval
- Summary measures of MBC history, including:
 - Whether cancer is primary or recurrent diagnosis.
 - Site and grade of disease.
 - Lymph node involvement (including number of lymph nodes) at initial BC diagnosis and by de novo status
 - Oestrogen-receptor, progesterone-receptor and HER2 status at initiation of disease

PFIZER CONFIDENTIAL

- Oestrogen-receptor, progesterone-receptor and HER2 status in the metastatic setting
- Proportion of patients (non de-novo metastatic only) who had a rebiopsy
- Oestrogen-receptor, progesterone-receptor and HER2 status at recurrence of disease out of those patients who were rebiopsied.
- Tumour stage at initial disease diagnosis and by de novo status
- Nodal status at initial disease diagnosis and by de novo status
- Metastatic at initial disease diagnosis and by de novo status
- Tumour size at initiation of disease and by de novo status
- Tumour grade at initiation of disease and by de novo status
- Proportion of patients who had Ki67 measured
- Summary of Ki67 values out of those patients with Ki67 measured.
- ECOG performance score at initial disease diagnosis
- ECOG performance score at recurrent disease diagnosis
- ECOG score at metastatic diagnosis
- Type of recurrence
- Number of metastatic sites.
- Location of metastases
 - Non-visceral location of metastases
 - Metastatic sites with locoregional recurrence
- Duration of BC disease at initiation of palbociclib.
 - Defined as date of diagnosis to date of initiation of palbociclib.
- Treatment history of MBC
 - Proportion of patients treated with chemotherapy in the neoadjuvant or adjuvant setting
 - Chemotherapy name
 - Proportion of patients treated with chemotherapy in the advanced/disease modification/metastatic setting
 - Chemotherapy name

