 - Number of lines of prior chemotherapy for metastatic disease
 - Proportion of patients for whom an LHRH was used
 - Proportion of patients treated with endocrine therapy in the neoadjuvant or adjuvant setting
 - Endocrine therapy name
 - Proportion of patients treated with endocrine therapy in the advanced/disease modifying/metastatic setting
 - Endocrine therapy name
 - Number of lines of prior endocrine therapy for metastatic disease
- Proportion of patients treated with radiotherapy in the advanced/disease modifying/metastatic setting
- Concomitant medications (defined as medications prescribed whilst on palbociclib)
- Concomitant medications prescribed alongside goserelin

PFIZER CONFIDENTIAL

- Number of prior treatments in the metastatic setting, all prior therapies as well as chemotherapy/endocrine therapy combined and separately

[figure not shown]
Secondary Objective 1: To describe treatment pattern (as per licence/IPP requirement); including the proportion of patients with dose modification and who switch treatment 1, 2 and 3 years after palbociclib initiation, and median time to dose modification and treatment discontinuation ('drug survival'). For patients who progress, to describe the 1st /2nd /3rd line of treatment after progression.

- Summary measures of palbociclib treatment patterns including:
 - Starting Dose.
 - Endocrine partner prescribed alongside palbociclib
 - Proportion of patients with dose reductions at 1, 2 and 3 years after initiation.
 - Proportion of patients with palbociclib treatment discontinuation at 1, 2 and 3 years after initiation.
 - Reasons for discontinuation of palbociclib
 - Proportion of patients with temporary discontinuations
 - Time to dose reduction in number of days (from start of treatment) – 1st line treatment group only
 - Time to palbociclib discontinuation ('drug survival') in number of days (from start of treatment) in those patients permanently discontinuing palbociclib
 - Reasons for discontinuation.
 - 1st, 2nd, and 3rd line of treatment after progression: number of patients prescribed each medication, dose, and length of treatment.
- Description of the number of patients which are being prescribed as per posology of treatment.
 - Number of completed 28-day cycles per patient.
 - Proportion of patients co-administered letrozole at palbociclib initiation.
 - Proportion of patients co-administered fulvestrant at palbociclib initiation.

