between 50 and 65 years old and aged 65 and over). Disease free interval was defined as the time from last known date the patient was on (neo)adjuvant hormone therapy to the date of metastatic breast cancer diagnosis (non de novo patients only). Disease free interval was presented as a categorical variable as per section 8.1.2 (Groups: less than or equal to 12 months and greater than 12 months). Time from letrozole to palbociclib initiation was presented as a quantitative variable as per section 8.1.1 for the first line palbociclib added group only. Time from letrozole was calculated by subtracting the start date of letrozole (ongoing at palbociclib initiation) from the date of palbociclib initiation. Number of metastatic sites was presented as a categoric variable as per section 8.1.2 (Groups: 1,2,3, 4 or more). Number of lines of prior endocrine therapy and chemotherapy prescribed for metastatic disease were presented as quantitative variables as per section 8.1.1. All other variables, aside from those named in this paragraph or the paragraph directly above were analysed as categoric variables as per section 8.1.2.

8.2.2 Secondary Objective 1: To describe treatment pattern (as per licence/IPP requirement); including the proportion of patients with dose modification and who switch treatment at 1 and 2 years after palbociclib initiation, and median time to dose modification and treatment discontinuation ('drug survival'). For patients who progress, to describe the 1st /2nd /3rd line of treatment after progression.

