Proposed: Starting and mean dose of palbociclib and subsequent treatments after progression, length of treatments and time to dose reduction and discontinuation of palbociclib in days will be summarised as quantitative variables (see section 8.1.1). Times will be calculated in days through subtracting the time of first dose reduction/discontinuation from the date of palbociclib initiation. Treatment after progression and reasons for discontinuation, the proportion of patients completing a daily cycle, having dose reductions, treatment discontinuation and being co-administered letrozole and fulvestrant at palbociclib initiation will be summarised as categorical variables using frequencies and percentages (see section 8.1.2). Reasons for discontinuation of palbociclib will be presented as categorical data (see section 8.1.2) The proportions of patients with dose reductions and discontinuation will be calculated separately at 1 and 2 years after palbociclib initiation. Quantitative discrete variables (such as the number of completed cycles per patient) will be summarised using a combination of the approaches described in sections 8.1.1 and 8.1.2, if appropriate.

Actual: Starting dose of palbociclib was presented as a categoric variable as per section 8.1.2. Endocrine partner prescribed alongside palbociclib, proportion of patients with recorded dose reductions, proportion of patients who discontinued palbociclib and the associate reasons, proportion of patients with temporary interruptions to palbociclib treatment were presented as categoric variables as per section 8.1.2. Time to dose reduction was presented as a categoric variable as per section 8.1.2 (Categories: Patient did not have a dose reduction, dose reduction occurred within 3 months of palbociclib initiation, dose reduction occurred between 3 and 6 months after palbociclib initiation and dose reduction occurred over 6 months after palbociclib initiation). Number of patients

PFIZER CONFIDENTIAL

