prescribed treatment in the 1st, 2nd, and 3rd line after palbociclib discontinuation was presented as a categoric variable as per section 8.1.2. Dose, duration of subsequent treatments and number of completed 28-day cycles per patient were presented as quantitative variables as per section 8.1.1. Number of completed 28-day cycles (categories: 1-6 cycles, 7-12 cycles, 13-18 cycles, 19-24 cycles, 25-27 cycles and No completed cycles) and the proportion of patients co-administered letrozole or fulvestrant were presented as categoric variables as per section 8.1.2. All other endpoints were evaluated as proposed.

8.2.3 Secondary Objective 2: To describe overall survival and progression-free survival, response (CR, PR), stable disease. This includes estimating the proportion of patients achieving those endpoints at 1 and 2 following palbociclib initiation: median survival, time to response and duration of response. In patients who respond to treatment, to describe PR and CR using “swimmer plots”.

Proposed: For the estimation of the proportion of patients alive, and free from disease progression, the denominator will be all patients known to be alive at the selected time-points (e.g., 1 years, 2 years, and 3 years). For the estimation of the proportion of patients achieving PR, CR and with stable disease at the selected time-points (1 years and 2 years), the denominator will be all patients with at least one assessment of response (CR / PR / no response or stable disease / progressive disease) in the past year.

[figure not shown]
Actual: Proportion of patients free from disease progression, are alive, achieved PR, CR or stable disease were analysed separately at the 2-year timepoint only. Length of follow-up, and time to best response and first response were presented as quantitative variables as per section 8.1.1. Best response to palbociclib, overall and by de novo and relapse status was treated as a categoric variable and analysed according to section 8.1.2.

8.2.4 Secondary Objective 3: To describe the occurrence of neutropenia during the first-year post-initiation observation period.

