Relevant comorbidities documented within baseline period (to include all individual components of the Charlson	✓		✓	

PFIZER CONFIDENTIAL

Variables	Study time points			
	Baseline (From disease diagnosis to index date)	Index date	Post- initiation observatio n period	Other
comorbidity index, to be further defined in full in the eCRF).				
Date of start and end of concomitant medication treatment: letrozole, fulvestrant, osteo-strengthening drugs (denosumab, zometa), other (all medications to be included in eCRF)	✓		✓	
First 3 lines of medications after palbociclib discontinuation			✓	
Haemoglobin results to be extracted pre-first cycle, on day 1 of each cycle of treatment, on day 15 into cycles 1 and 2 and day 22 if available	✓	✓	✓	
White cell counts to be extracted as above	✓	✓	✓	
Absolute neutrophil counts to be extracted as above	✓	✓	✓	
Platelet counts to be extracted as above	✓	✓	✓	
Aspartate transaminase levels to be extracted as above	✓	✓	✓	
Alanine transaminase levels to be extracted as above	✓	✓	✓	
Alkaline phosphatase levels to be extracted as above	✓	✓	✓	
Calcium levels to be extracted at pre-first cycle, then at each cycle, in the first year following initiation	✓	✓	✓	
Phosphate levels to be extracted as above	✓	✓	✓	
Calls from patient to CNS: dates and reason			✓	
BC-related inpatient admissions to hospital: planned (elective), A&E, reasons, duration (dates of entry and discharge)			✓	
BC-related outpatient admission: dates, reason			✓	
Progression: sites, dates			✓	

PFIZER CONFIDENTIAL

Variables	Study time points			
	Baseline (From disease diagnosis to index date)	Index date	Post- initiation observatio n period	Other
AE: Neutropenia (Y/N), date start and end, grade			✓	
AE: Febrile Neutropenia (Y/N), date start and end			✓	
AE: Diarrhoea (Y/N), date start and end, grade			✓	
AE: Nausea (Y/N), date start and end, grade			✓	
AE: Vomiting (Y/N), date start and end, grade			✓	
Death: date, cause				✓

Note: All dates are DD/MM/YYYY for all patients, except for date of birth (MM/YY)

PFIZER CONFIDENTIAL

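### Secondary Objective 1 asks for treatment lines after progression in patients who progress, but SAP 8.2.2 tabulates lines after palbociclib discontinuation with no stated restriction to patients who had progressed

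*SAP*

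**What the plan says.** The objective, as repeated in the heading of SAP 8.2.2, fixes both a population and a starting event: "For patients who progress, to describe the 1st /2nd /3rd line of treatment after progression". Protocol section 8 and SAP 2.2 say the same. The endpoint in SAP section 6 is "1st, 2nd, and 3rd line of treatment after progression: number of patients prescribed each medication, dose, and length of treatment", and the endpoint column of protocol 9.3 matches it. SAP section 6 says of its own list: "This list is designed to reflect the analyses conducted". The Proposed paragraph of 8.2.2 also starts from progression, naming "Treatment after progression and reasons for discontinuation" among its categorical summaries.

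The Actual paragraph changes the starting event: the number of patients "prescribed treatment in the 1st, 2nd, and 3rd line after palbociclib discontinuation was presented as a categoric variable". It then summarises the dose and duration of subsequent treatments without naming a population.

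The data were specified on that second basis from the outset. The variable column of protocol 9.3 lists "First 3 lines of medication after palbociclib discontinuation: name, dose and length of treatment", and the dataset table in SAP section 11 lists "First 3 lines of medications after palbociclib discontinuation".

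**The concern.** Stopping palbociclib and progressing are different events. A patient may stop for another reason, and what that patient receives next is not a post-progression line. If such patients are counted, the table answers a wider question than the objective asks. The drug distribution, doses and durations would then combine two clinical situations, and line numbers could be displaced. A reader of the final report who wants to know what follows progression on palbociclib could not separate the two.

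**Working it through.** No figure in the plan bears on this endpoint, so the check is a comparison of text followed by a classification of patients.

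**Step 1: the starting event and population at each place**

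| Place | Lines counted from | Population stated |
|---|---|---|
| Protocol 8, SAP 2.2, SAP 8.2.2 heading | progression | patients who progress |
| Protocol 9.3, endpoint column | progression | none beyond the objective it sits under |
| Protocol 9.3, variable column; protocol Annex 3; SAP 11 | palbociclib discontinuation | none |
| SAP 6 | progression | none beyond the objective it sits under |
| SAP 8.2.2 Proposed | progression | none |
| SAP 8.2.2 Actual | palbociclib discontinuation | none |

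The summary table in SAP 8.2.9 does not settle the matter. It has no row for subsequent lines, and its treatment-pattern rows use the full analysis set, overall and by treatment line. The duration-of-response row of the same table does name a restricted population (responders).

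**Step 2: does the plan treat the two events as one?** It does not. The Actual paragraph separately tabulates the "proportion of patients who discontinued palbociclib and the associate reasons", so more than one reason is expected. Progression sites and dates are a separate entry in the dataset tables. Nowhere is discontinuation equated with progression.

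**Step 3: what each starting event does to a patient**

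- Progresses, stops, starts a new therapy: the same line number either way, if nothing was added between progression and stopping.
- Stops without progression, starts a new therapy, does not progress: in the discontinuation table, outside the objective.
- Stops without progression, starts one new therapy, then progresses and changes again: the first line after progression is tabulated as the second. The third would be the fourth after discontinuation, beyond the three lines collected.
- Stops for another reason but progresses before the next therapy: a true post-progression line, although the recorded reason is not progression.
- Progresses, continues palbociclib, stops later: enters the table at the later stop. A therapy added in between is not counted from progression.
- Progresses and is still on palbociclib at the end of data: not in the table, and has had no line after palbociclib.

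**Step 4: size.** Among patients who stop, let *q* be the share whose recorded reason is not progression. Let *a* and *b* be the probabilities of starting a next therapy in that group and in the remainder. Let *c* be the share of next-line starters in the first group who had progressed by that start. Taking everyone in the remainder as progressed, the share of first-line entries outside the objective is

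*s* = *q·a*·(1 − *c*) / [*q·a* + (1 − *q*)·*b*].

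None of these four quantities is in the documents. Purely as an assumption, take *q* = 0.15 to 0.30 with *a* = *b*, so that *s* = *q*(1 − *c*):

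- *c* = 1: *s* = 0.
- *c* = 0: *s* = 0.15 to 0.30.

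So even a known *q* would leave a range from zero to *q*. If *a* exceeds *b*, *s* can be larger than *q* when *c* is small.

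**The case against.** The best defence is that the Actual paragraph names a starting event, not a population. It stands under a heading confined to patients who progress, and SAP section 6, said to mirror the analyses done, still refers to progression. On that reading the table holds only progressors, with lines numbered from the stop. The reading is open, and it means that inclusion of everyone who stopped, for any reason, cannot be stated as fact. That is inferred from the absence of a restriction. What the defence cannot do is show that a restriction was applied. The closing statement that other endpoints followed the proposal does not help, because subsequent lines are among the endpoints that paragraph restates.

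Three other points in the plan's favour:

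- Protocol 9.7 lets the SAP modify the analyses and requires an amendment only for major changes to the primary endpoint. The change is therefore permitted, but it is neither flagged nor explained.
- SAP section 9 refers to table shells held elsewhere. Mislabelling cannot be shown, and a table titled by discontinuation would be correctly labelled.
- Reasons for discontinuation are reported, so a reader will see how many stops were attributed to progression, though not which later lines belong to them.

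Three stronger inferences are tempting and not supported:

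- *The error equals the share of stops not attributed to progression.* Step 4 shows otherwise: such a patient may progress before the next therapy, and the groups may start a next therapy at different rates.
- *Patients who progress and stay on palbociclib are lost.* They enter if they later stop; until then they have no line after palbociclib.
- *The objective goes unanswered.* Progressors who stopped are in the table on either reading. The problem is that others may be there with them.

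**Conclusion.** The inconsistency is real, and it lies both within the SAP and between the two columns of protocol 9.3. Taken literally, 8.2.2 Actual can place patients without progression among the lines meant to follow progression, and can displace line numbers for those who progress later. This conclusion rests on the paragraph being applied without an unstated restriction. The size cannot be computed from the documents, and it is zero only if every patient with a next line had progressed before starting it. The consequence is moderate: this is one descriptive component of a secondary objective in a study with no hypothesis test. It should still be corrected, because the separation is cheap and the stated objective depends on it.

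**What to change.** In SAP 8.2.2:

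1. Tabulate subsequent lines (medication, dose, duration) separately for patients with documented progression on or before the start of the next line and for those without, each with its own denominator. Classify by progression date, not by reason for stopping alone, and say which eCRF record supplies that date.
2. Use the first group for the objective, counting its lines from progression.
3. Label any table of all discontinuers as after palbociclib discontinuation.
4. Report the number who progressed while continuing palbociclib.
5. Reconcile the wording of protocol 9.3, SAP section 6, and the heading and Actual paragraph of SAP 8.2.2.

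The cost is one stratified table. Progression dates, discontinuation reasons and subsequent medications are already in the dataset, so no new collection is needed. The price is smaller denominators in each stratum, most noticeably at the second and third lines.

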8.1.1 Analysis for quantitative data

Quantitative data will generally be analysed using basic summary statistics of central tendency (including means and medians) and dispersion (including standard deviations, the interquartile range [IQR] and the range). If distributions are normally distributed (evaluated through inspection of histograms), 95% confidence intervals will be calculated assuming a normal distribution, otherwise the median and IQR will be presented instead. Where appropriate, i.e., for ordinal endpoints frequency and percentages will be presented along with summary statistics.

PFIZER CONFIDENTIAL

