8.2.9 Summary of Analyses

Outcome	Analysis Set	Supports Protocol Objective Number	Subgroups	Statistical Method	Missing Data
Summary of age at initiation of palbociclib	Full Analysis set	Primary Objective	Overall and treatment Line	Calculated by subtracting Date of palbociclib initiation from Date of Birth. Summary statistics calculated (incl. Mean/Median/SD/IQR/Range)	Day of birth assumed to be the 15 th . If month is missing, birthday assumed to be 1 st July. Otherwise excluded.
Distributions of categorical, binary, and ordinal demographical and clinical characteristics	Full Analysis set	Primary Objective	Overall and treatment Line	Frequency tables and percentages	Excluded
Summary measures of MBC statistics	Full Analysis set	Primary Objective	Overall and Treatment Line	Frequency tables and percentages Summary statistics for Ki67 proliferation index (incl. Mean/Median/SD/IQR/Range)	Excluded
Duration of MBC at palbociclib initiation	Full Analysis set	Primary Objective	Overall and Treatment Line	Calculated by subtracting Date of palbociclib initiation from Date of MBC diagnosis. Summary statistics calculated (incl. Mean/Median/SD/IQR/Range)	Standard imputation for dates (section 7), otherwise exclude.
Treatment for MBC diagnosis prior to palbociclib initiation	Full Analysis set	Primary Objective	Overall and Treatment Line	Frequency tables and percentages	Excluded
Summaries of comorbidities and Charlson comorbidity index of patients at palbociclib initiation	Full Analysis set	Primary Objective	Overall and Treatment Line	Frequency tables and percentages for each comorbidity type Summary statistics calculated (incl. Mean/Median/SD/IQR/Range) for Charlson comorbidity index	Excluded
Palbociclib prescribed as on or off-label	Full Analysis set	Primary Objective	Overall and Treatment Line	Frequency tables and percentages	Excluded
Summary measures of palbociclib treatment patterns	Full Analysis set	Secondary Objective 1	Overall and Treatment Line	Frequency tables and percentages for proportions and categorical variables such as proportion of patients with dose reductions or discontinuation and reasons for discontinuation Summary statistics calculated (incl.	Excluded

PFIZER CONFIDENTIAL

				Mean/Median/SD/IQR/Range) for doses, time to dose reduction and discontinuation and length of treatment	

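### Durations of the 1st, 2nd and 3rd lines after palbociclib are summarised with no rule for courses still running at the 2-year cut, which biases them short

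*SAP*

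**What the plan says.** The endpoint list in SAP section 6 (Secondary Objective 1) includes "1st, 2nd, and 3rd line of treatment after progression: number of patients prescribed each medication, dose, and length of treatment". Protocol 9.3 names the data item behind it: "First 3 lines of medication after palbociclib discontinuation: name, dose and length of treatment".

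SAP 8.2.2 gives the method twice. The Proposed text says "length of treatments and time to dose reduction and discontinuation of palbociclib in days will be summarised as quantitative variables", and the Actual text says "Dose, duration of subsequent treatments and number of completed 28-day cycles per patient were presented as quantitative variables", by reference to section 8.1.1. Section 8.1.1 reads "Quantitative data will generally be analysed using basic summary statistics of central tendency (including means and medians) and dispersion", and says nothing about incomplete durations.

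The summary table in SAP 8.2.9 has a row for palbociclib treatment patterns that lists "Mean/Median/SD/IQR/Range) for doses, time to dose reduction and discontinuation and length of treatment". Its missing-data column says such values are excluded.

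SAP 5.1 and 8.1 set the analysis on 2-year follow-up. The censoring rules in Protocol 9.7 and SAP 8.2 cover survival, progression and response. The Kaplan-Meier list in Protocol 9.7 covers PFS, OS, time to best response, and time to palbociclib dose modification and discontinuation. SAP 8.1.3 allows Kaplan-Meier for survival-related endpoints. None of these names the duration of a later line.

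**The concern.** A later line begins only after palbociclib has stopped, and the 2nd and 3rd lines only after the line before has stopped. The time in which each can be observed is what remains of the 24 months. If the patient is still on that line at the cut, or when follow-up is lost, the data show only that the course lasted at least that long. An ordinary median cannot use that information.

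Describing the treatment sequence after progression is part of Secondary Objective 1, and length of treatment is a listed endpoint for the final report. If the durations are systematically short, treatment after palbociclib looks briefer than it was. A reader cannot correct for this without knowing how many courses were ongoing.

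**Working it through.** The documents state no figure to reproduce: the study is descriptive and gives no expected later-line duration. The check is of direction first, then of size under stated assumptions.

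**Direction.** Let D be the true length of a course and W the time from its start to the cut.

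- Entered up to the cut: the recorded value is min(D, W), which never exceeds D.
- Left out: only courses with D ≤ W remain. If D and W are independent, the density of the retained values is proportional to f(t)·Pr(W ≥ t). The second factor falls with t, so the retained values are shorter than D for any distribution.

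Both effects grow as W shrinks, which is the case for each successive line.

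**Inputs for size.**

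- Cut C = 24 months (SAP 5.1 and 8.1).
- Median time on palbociclib m_P = 16, 20 or 25 months (assumption). The top value is near the 24.8-month median PFS quoted in Protocol section 7, which is PFS and not time on treatment.
- True next-line median m_D = 5 or 9 months (assumption).
- Exponential, independent times; the next line starts when palbociclib stops.

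**Formulas, among patients who start the next line before C.**

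- Share ongoing = [m_D/(m_P − m_D)] × [2^(−C/m_P) − 2^(−C/m_D)] / [1 − 2^(−C/m_P)].
- Truncated median: the t that solves 2^(−t/m_D) × [1 − 2^(−(C−t)/m_P)] / [1 − 2^(−C/m_P)] = 0.5.
- Completed-only median: the median of the density proportional to 2^(−t/m_D) × [1 − 2^(−(C−t)/m_P)] on 0 to C.

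**Worked case, m_P = 25 and m_D = 9.**

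- 2^(−24/25) = 0.514 and 2^(−24/9) = 0.157.
- Share ongoing = (9/16) × (0.514 − 0.157)/(1 − 0.514) = 0.5625 × 0.734 = 0.41.
- At t = 6.15 the truncated survival is 0.623 × 0.803 = 0.50, so the reported median is about 6.2 months.
- The completed-only median, found numerically, is 4.9 months.

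**Next line, over m_P = 16 to 25.**

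| True median (months) | Ongoing at cut | Median if truncated | Median if dropped |
|---|---|---|---|
| 5 | 22-25% | 4.0-4.2 (16-20% low) | 3.7-3.8 (24-26% low) |
| 9 | 39-41% | 6.2-6.5 (28-31% low) | 4.9-5.1 (43-46% low) |

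**All three lines.** A simulation of 400,000 patients per scenario used m_P = 24.8 and a true median of 6 months for every line.

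| Line | Ongoing | Truncated | Dropped | Kaplan-Meier |
|---|---|---|---|---|
| 1st | 29% | 4.6 | 4.1 | 6.0 |
| 2nd | 39% | 4.1 | 3.5 | 6.0 |
| 3rd | 47% | 3.5 | 3.0 | 6.0 |

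With palbociclib medians of 12 to 24.8 months and later-line medians of 4 to 12 months, the ordinary median was below the truth in every scenario. If truncated, it was about 13-39% low for the 1st line and 25-64% low for the 3rd. If dropped, it was 18-55% and 33-71% low. Kaplan-Meier with ongoing courses censored at the cut came within about 0.1 month of the truth throughout. A 36-month cut reduces the bias but does not remove it: in the 6-month scenario the truncated medians become 5.2, 4.8 and 4.4.

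**The case against.** The strongest reply is that the plan is silent on ongoing courses and that a reader fills the gap. Three stronger readings are tempting, and the documents support none of them.

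- **That ongoing courses are known to be cut short, or known to be dropped.** No text says which. The exclusion entry in SAP 8.2.9 concerns missing data, and nothing says an ongoing course is coded as missing. That row is also labelled palbociclib treatment patterns, so it reaches later lines only through the grouping in section 6. The firm anchor is 8.2.2.
- **That most later lines start late in the window.** The documents give no start times. Under the exponential assumption the share of next lines starting in the first 12 months is 1/(1 + 2^(−12/m_P)), which is 63% at m_P = 16 and 58% at 25. The bias does not need late starts.
- **That the data cannot support censoring.** Protocol 9.3 leaves detail to the eCRF, and SAP section 9 places the table shells in other documents. Start and stop dates, or a count of ongoing courses, may already exist.

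It is also fair to say that the magnitudes rest on assumed durations. With a 5-month true median, truncation costs only 0.8-1.0 month. The counts of patients on each drug are not distorted, and the study tests no hypothesis.

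What does not fall is the method. SAP 8.2.2 assigns these durations to 8.1.1 in both its Proposed and Actual text, and neither likely way of applying 8.1.1 to an ongoing course gives an unbiased duration. Reporting the number ongoing and labelling durations as observed within two years would help the reader, but would leave the estimate short.

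**Conclusion.** The point holds. The stated method for the duration of 1st, 2nd and 3rd line treatment after palbociclib does not suit right-censored data, and nothing elsewhere in the protocol or SAP corrects it. For truncation, the downward direction needs no distributional assumption. For dropping, it needs the remaining window to be independent of course length. The growth from the 1st to the 3rd line assumes broadly similar true durations across lines.

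The size is illustrative only. In the next-line scenarios above, the median is understated by roughly one sixth to one third if ongoing courses are truncated, and by roughly a quarter to nearly one half if they are dropped. This affects one descriptive component of a secondary objective, so it should be corrected, but the primary objective, PFS and OS do not depend on it.

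**What to change.** In SAP 8.2.2 and 8.2.9, estimate the duration of each later line by Kaplan-Meier from the start of that line. The event is stopping the line or death. Courses still running are censored at the cut or at the last record showing treatment. For each line report the number of patients starting, the number ongoing, and the median with its 95% CI. Give later lines their own row in 8.2.9.

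Use start and stop dates from the eCRF if they are held there. Add a stop-date or ongoing field only if they are not.

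The cost is a change of SAP wording, a rerun of one table and possibly one added field. One limit remains: the 2nd and 3rd line estimates describe only patients who reached that line within two years. They stay approximate if durations are correlated within patients, because the time left for a later line then depends on how long earlier treatment lasted. The counts per line keep this visible.
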